12.0 CRITERIA FOR THERAPEUTIC RESPONSE/OUTCOME ASSESSMENT

The null hypothesis is that GDT in patients undergoing liver resection does not alter the incidence of postoperative complications. A 15% decrease (from 30% to 15%) in the

MEMORIAL SLOAN-KETTERING CANCER CENTER IRB PROTOCOL

IRB#: 12-056 A(4)

incidence of 30-day complications will be considered clinically significant and will represent the primary outcome measure. The incidence of these will be assessed after each patient's postoperative visits.

Secondary outcomes include the impact of GDT on low cardiac output time, total volume of fluid used perioperatively, the requirement for blood transfusion, the total dose of vasoactive drugs, end-organ perfusion markers and the net fluid balance 48 hrs postoperatively.

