2.0 OBJECTIVES AND SCIENTIFIC AIMS

Primary objective:

- Evaluate the impact of goal-directed fluid management on the incidence of overall postoperative morbidity in patients undergoing liver resection.

Secondary Objective:

- Assess the impact of GDT compared to standard fluid therapy on the total time patients experience low cardiac output perioperatively (i.e. intraoperative and in the first 24 postoperative hours).
- Assess the impact of GDT compared to standard fluid therapy on the total volume of fluid given intraoperatively and during the first 72 hrs postoperatively.
- Assess the impact of GDT compared to standard fluid therapy on the requirement for blood transfusion.
- Compare the total dose (mcg/kg) of vasoactive agents used in the first 24 hrs between the standard management and GDT groups.
- Measure the difference in end-organ perfusion markers between GDT and standard therapy for fluid management.
- Assess the impact of GDT compared to standard fluid therapy on net fluid balance for the total admission time.
- Assess the impact of GDT compared to standard fluid therapy on the systemic inflammatory response.

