Adequacy of postoperative resuscitation will be determined by comparing end-tissue perfusion variables as well as inflammatory markers (a multiplex cytokine panel that includes IL-2, IL-4, IL-6, IL-10, IL-17, TNF α , and INF γ) before skin incision (as baseline), at the beginning of resuscitation phase, at time of completion of the case and the morning of the 2

MEMORIAL SLOAN-KETTERING CANCER CENTER IRB PROTOCOL

IRB#: 12-056 A(4)

first postoperative days. **See Table 2 – section 10.0 Evaluation during treatment/Intervention.** After evaluation of inflammatory response in the initial set of 20 randomized patients, it was determined that no statistically significant difference was likely to be found between the 2 randomization arms and the protocol was amended to discontinue the blood collections and cytokine analysis.

Continuous assessment of cardiac output as determined by the arterial waveform analysis, total fluid therapy, (crystalloid and colloid), units of pRBCs, total dose (mcg/kg) of each vasoactive agent, cumulative fluid balance and the incidence of overall 30-day postoperative complications will be recorded. These are defined in the MSKCC Adverse Events Program and organized by categories reflecting organ systems (listed below) and further subdivided into specific complications within those and graded as reflected in appendix 2. A detailed listing of complications and grading can be found at: <http://vssurpweb1/AdverseEvents>.

Categories

*None at 30 days post-op

Cardiovascular System

Endocrine System

Gastrointestinal System

General

Genitourinary System

Head and Neck

Hematologic or Vascular System

Infection

Metabolic

Musculoskeletal System

Nervous System

Pain

Pulmonary System

Wound or Skin

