10.0 EVALUATION DURING TREATMENT/INTERVENTION

- Preoperative data will be collected and recorded: date of birth, weight, height, complete metabolic panel, complete blood count, coagulation profile.
- Standard intraoperative monitoring will be carried out for all patients.
- GDT patients will also be monitored by CO, SV and SVV. These data will similarly be obtained and recorded for the patients in the standard management group but it will not be available for the treating practitioners.
- Further measures of end-tissue perfusion will be assessed with arterial lactate levels and DO₂ (oxygen delivery) at baseline (before incision), at completion of the resection phase (intraoperatively), upon arrival to PACU (0 hours postoperatively), and on the morning of POD #1.
- Assessment and recording of all intraoperative and postoperative complications; the latter being considered as those occurring on or after postoperative day 1 until postoperative day 30. Complications occurring intraoperatively and after surgery on

MEMORIAL SLOAN-KETTERING CANCER CENTER
IRB PROTOCOL

IRB#: 12-056 A(4)

the same day, are most likely technical in nature and will be considered perioperative complications in the analysis.

- Estimated operative blood loss.
- Cumulative volume used for resuscitation will be recorded (stratified by colloids and crystalloids)
- Total dose (mcg/kg) of pressors, inotropes or vasodilators used will be recorded and stratified by specific drugs.
- Volume and type of blood products transfused.
- Daily comprehensive metabolic panel, complete blood count (these will be recorded for seven days or until discharged if discharged earlier).
- Daily coagulation panel, discontinued by POD 3 if normal.
- Volume and type of fluid intake and output until POD 7 or patient tolerates oral intake of fluids > 400 ml/24 hrs
- Daily nasogastric tube drainage volume (if used) and length of NG drainage
- Daily weight until POD 7 or until patient tolerates oral intake of fluids > 400 ml/24 hrs.
- Day of tolerating oral intake of fluids > 400ml/24hrs
- Day of IV ≤ KVO
- Day of tolerating oral intake of solids
- Day of passage of flatus
- Day of foley removal.
- Day of passage of feces
- Day of discharge

Table 2. Details hemodynamic and laboratory values obtained at different stages. For laboratory values a 30 minute variation will be allowed to account for early or delayed sample collection in the PACU and/or surgical ward.

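### Net fluid balance has two conflicting windows, and the data collection described does not reliably cover either it or the 24-hour low-cardiac-output time (secondary endpoints only)

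*Combined protocol and SAP*

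**What the plan says.** **Net fluid balance.** Section 2.0 lists the secondary objective as "net fluid balance for the total admission time". Section 12.0 lists the outcome as "the net fluid balance 48 hrs postoperatively". Section 4.1 says "cumulative fluid balance and the incidence of overall 30-day postoperative complications will be recorded" and gives the balance no end point.

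Section 10.0 says what is collected: "Volume and type of fluid intake and output until POD 7 or patient tolerates oral intake of fluids", with the threshold set at more than 400 ml in 24 hours. Daily weight, the natural cross-check on fluid balance, has the same stop: "Daily weight until POD 7 or until patient tolerates oral intake of fluids". Neither item says whether the first or the last of the two events ends recording. For the daily laboratory panels, the same section uses a rule that does not depend on recovery: "these will be recorded for seven days or until discharged if discharged earlier".

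**Fluid volume.** Section 2.0 gives the volume endpoint a window of 72 hours after surgery. Section 12.0 calls it only perioperative.

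**Low-cardiac-output time.** Section 2.0 counts it during the operation and for 24 hours afterwards. Section 4.1 takes cardiac output from the arterial waveform. Section 9.0 keeps patients in the PACU until the next morning and has the arterial line taken out when they go to the ward.

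**Analysis.** Section 14.0 compares the non-categorical secondary endpoints with a rank-sum test. It states no window and no rule for incomplete observation.

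**The concern.** With two windows in current text, the net-balance endpoint is not fixed in advance. The choice could be made after the data are seen, and the two versions could give different answers.

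The recording stop adds a second problem. Oral intake is a recovery event that happens after randomisation, and fluid strategy may influence it. Section 3.0 itself cites a colorectal trial in which guided fluid therapy was followed by earlier return of bowel function. If recording ends when the patient starts to drink, its length depends on an outcome of treatment.

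Low-cardiac-output time is a total, so it can only accumulate while the line is in place. If monitored hours differ between patients, the total partly reflects the time of day at which surgery ended.

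Fluid balance and haemodynamics are what this intervention acts on directly. Intake and output that are not recorded at the time may not be recoverable later.

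**Working it through.** The plan gives no figure for this point, so there is none to reproduce. The sample size of 270 does not enter.

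**(a) Net fluid balance.** Let T be the time at which oral intake first exceeds 400 ml in 24 hours. Section 10.0 can be read in two ways:

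| Reading of the stop | Recording ends at | Admission-long balance (Section 2.0) | 48-hour balance (Section 12.0) |
|---|---|---|---|
| Whichever comes first | the earlier of day 7 and T | Missing for anyone still in hospital after the earlier event | Cut short if T falls before 48 h |
| Whichever comes last | the later of day 7 and T | Missing for anyone still in hospital after the later event | Covered, since day 7 lies beyond 48 h |

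Neither reading supplies the Section 2.0 endpoint for every patient. Only the second reliably supplies the Section 12.0 endpoint. Daily weight stops by the same rule, so it cannot fill the gap. The documents do not say how often T falls before 48 hours.

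The 72-hour fluid volume is less exposed. Under Section 9.0, ward maintenance fluid ends at the same oral threshold, so little intravenous maintenance should be missed after the stop. Later boluses may fall under a separate item with no stop: "Cumulative volume used for resuscitation will be recorded". The plan does not say whether ward boluses count there.

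**(b) Low-cardiac-output time.** Let E be the clock hour at which surgery ends and R the clock hour at which the line is removed next day.

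Observed postoperative hours = 24 − E + R

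This reaches 24 only if E ≤ R.

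- *From the text alone.* Removal in the morning means R < 12, so any operation ending at noon or later has fewer than 24 hours. Surgery ending at 14:00 gives fewer than 24 − 14 + 12 = 22 h. Surgery ending at 18:00 gives fewer than 24 − 18 + 12 = 18 h.
- *With assumed clock times* (the documents give none). Take E from 11:00 to 19:00 and R from 06:00 to 10:00. The shortest case is 24 − 19 + 6 = 11 h (11/24 = 46%). The longest is 24 − 11 + 10 = 23 h (23/24 = 96%). For E = 15:00 and R = 08:00, 24 − 15 + 8 = 17 h (71%), with 7 h unobserved.

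Table 2 is cut off in the text available, so the absence of a cardiac-output row or time point is not used as evidence.

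**The case against.** The strongest case is that this is an editorial inconsistency. Section 4.1 promises cumulative balance without a stop. Section 9.0 has ward urine output assessed over 4- and 8-hour periods and weight gain considered from postoperative day 2, neither conditional on oral intake, so source data probably continue. The 24 hours may be loose wording for overnight monitoring: Section 12.0 gives this outcome no 24-hour window, and the legible stroke-volume row of Table 2 runs to the morning of day 1, in line with line removal. The line rule is the same in both arms, so unequal hours should add noise rather than bias.

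Much of this is fair, and it is why the point is minor. It does not remove the point. Section 4.1 sets no window and so cannot settle which is meant. The Section 9.0 checks are care rules and do not commit the study to recording balance. If overnight monitoring is what was meant, Section 2.0 still says otherwise, and overnight stays still differ in length.

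A reader might go further in two ways that the documents do not support:

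- *That the recording stop biases net balance by a calculable amount, or in favour of one arm.* The timing of oral intake, the intake and the urine output after the stop are not given. The net amount missed could have either sign.
- *That a proportion of monitored time would gain power over a raw total.* This depends on when low output occurs. If it is equally likely in every monitored hour, the raw total is the noisier measure. If it falls mainly in the first hours after surgery, later monitored hours dilute the proportion and the ranking reverses. The documents do not say which applies.

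**Conclusion.** The point holds as a minor one on secondary endpoints. The primary endpoint and the sample size are not affected.

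Three parts rest on the text alone. Sections 2.0 and 12.0 define different net-balance endpoints. Section 10.0 does not supply admission-long balance for stays past its stop on either reading. A 24-hour cardiac-output window cannot be complete for operations that end later in the day than the next morning's line removal.

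Two parts are conditional. Loss from the 48-hour balance requires that the earlier event governs and that the oral threshold is met before 48 hours. The 11 to 23 observed hours rest on assumed clock times.

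No size or direction of between-arm bias is claimed, and no gain in power.

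**What to change.** **(a) Net fluid balance.**

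- State one fixed window, in the same words, in Sections 2.0, 4.1, 10.0 and 12.0. A fixed window also avoids an endpoint whose length is set by length of stay.
- In Section 10.0, record intake and output in all inpatients through that window, and through 72 hours for the fluid-volume endpoint, or to discharge if sooner, regardless of oral intake. The section's laboratory rule already has this form.
- Give the 72-hour window in Section 12.0 as well, and say whether ward boluses count towards it.
- Say how urine output is recorded once the catheter is out; "Day of foley removal" is already collected.

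**(b) Low-cardiac-output time.**

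- Reconcile Section 2.0 with Section 9.0 by defining the endpoint over the period actually monitored, and report monitored hours by arm.
- State in Section 14.0 whether the analysis uses a proportion of monitored time or a fixed window common to all patients. Either is defensible; the choice should be made before the data are seen.

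**Cost.** A few sentences of protocol text and a little more routine charting in patients who drink early. Urine measurement will be less exact after catheter removal. Nothing here requires a change to line timing or to PACU or ward care.

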13.0 CRITERIA FOR REMOVAL FROM STUDY

At any point during the study, the attending surgeon or anesthesiologist may decide to go off protocol in their resuscitation strategy if they deem it necessary for patient safety.

Randomized patients will not be replaced for any reason. If a patient is transferred to the Intensive Care Unit, they will have that recorded as a complication and will be removed from the study. Management will continue in the patient's best interests and according to ICU guidelines.

14.0 BIOSTATISTICS

This is a randomized comparison of goal-directed compared to standard fluid management in patients undergoing liver resection. Primary endpoint is overall postoperative morbidity.

270 patients will be randomized 1:1 to the two arms. This sample size provides 80% power for detecting a 15% decrease in the proportion of overall postoperative complications (i.e regardless of grade of severity), assuming the standard arm will have a 30% complication rate (two-sided Type I error of 5%). It also allows for an interim analysis halfway through enrollment, using O'Brien-Fleming boundaries both for efficacy and futility. If $p \leq 0.005$ at the interim analysis enrollment will stop with the conclusion that goal-directed fluid management significantly decreases postoperative morbidity. If $p \geq 0.468$ at the interim analysis enrollment will stop with the conclusion that goal-directed fluid management does not significantly decrease postoperative morbidity. If $0.005 < p < 0.468$ then the trial will continue to full enrollment. With an approximate enrollment of 11 patients per month, accrual should be complete in 2 years.

Secondary endpoints will be compared between the two arms using the Wilcoxon rank-sum test, except for the categorical endpoints of blood transfusion and systemic inflammatory response, which will be compared using Fisher's exact test.

MEMORIAL SLOAN-KETTERING CANCER CENTER IRB PROTOCOL

IRB#: 12-056 A(4)

Since one of our main goals for this study is to establish what the individual amount of resuscitation is for each patient, tailored to their hemodynamic status, we decided to use their baseline value ± 2 standard variations as their homostatic stroke volume variation. An elevation above 2 standard deviations would be statistically unlikely to represent a normal variation of the measurement and will thus be considered a hemodincomically significant deviation from baseline.

15.0 RESEARCH PARTICIPANT REGISTRATION AND RANDOMIZATION PROCEDURES

15.1 Research Participant Registration

Confirm eligibility as defined in the section entitled Criteria for Patient/Subject Eligibility.

Obtain informed consent, by following procedures defined in section entitled Informed Consent Procedures.

During the registration process registering individuals will be required to complete a protocol specific Eligibility Checklist.

All participants must be registered through the Protocol Participant Registration (PPR) Office at Memorial Sloan-Kettering Cancer Center. PPR is available Monday through Friday from 8:30am – 5:30pm at [contact]. Registrations must be submitted via the PPR Electronic Registration System (<http://ppr/>). The completed signature page of the written consent/RA or verbal script/RA, a completed Eligibility Checklist and other relevant documents must be uploaded via the PPR Electronic Registration System.

15.2 Randomization

This is a single-blinded randomized trial. After eligibility is established and consent is obtained, patients will be registered in the Protocol Participant Registration (PPR) system.

Eligible patients will be consented for the trial prior to surgery. However randomization will not occur until the operating room. After the liver has been resected, intraoperative randomization will be done by envelopes. Randomization will be stratified by diagnosis (metastatic liver disease compared to primary disease where primary disease will encompass liver cancer and extrahepatic biliary cancer).

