4.0 OVERVIEW OF STUDY DESIGN/INTERVENTION

4.1 Design

Prospective single-blinded randomized trial. Eligible patients will be consented for the trial prior to surgery. However randomization will not occur until the operating room. After the liver has been resected, intraoperative randomization will be done by envelopes. Preoperative preparation and induction will be standard for all patients. In the OR all patients will have an arterial line placed preinduction and baseline hemodynamic data recorded from the Edwards EV1000 system. In the study, all intraoperative fluid therapy will be managed with the standard LCVP anesthetic technique for hepatic resection, and then at the completion of the resection all fluid therapy will be managed according to randomization arm (Goal-directed fluid therapy-**appendix 1** compared to standard fluid management- see detail below) for reconstruction and closure. In the postoperative phase, management will be standardized for both arms as outlines below.

During low central venous pressure (LCVP) anesthetic technique for partial hepatectomy, intraoperative fluid balance is divided in to two phases (as previously published)⁸:

- Prehepatic resection (the first phase), starts at anesthesia induction and ends at the completion of parenchymal transection and hemostasis. This phase takes advantage of fluid restriction and the vasodilatory effects of anesthetic drugs to provide LCVP anesthetic management. Fluid boluses and/or vasoactive drugs are administered at the discretion of the anesthesia provider to maintain systolic blood pressure > 90 mm Hg and urine output > 25 ml/hr while keeping the cvp <5 mmHg (currently, the vast majority of our patients do not require central line placement for the performance of liver resections. Low central venous pressure is assessed by the surgeon's direct assessment of the distention of the vena cava at the time of surgery). Maintenance fluid is 1cc/kg/hr.

Prior to proceeding to the second phase the intraoperative fluid management after the hepatic resection, patients will be randomized to either

Goal-directed fluid therapy (**see appendix 1**)

Standard fluid management (**see appendix 1**).

MEMORIAL SLOAN-KETTERING CANCER CENTER IRB PROTOCOL

IRB#: 12-056 A(4)

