- Posthepatic resection (the second phase), begins once the specimen has been delivered and hemostasis secured. During this phase, an attempt is made to return the patient to normovolemia. For our standard fluid management, blood loss is replaced volume to volume with albumin and crystalloid (6 cc/kg/hr x total operative time) will be infused to achieve the assumed fluid requirement (third space). After this fluid therapy, if BP<90mmHg or urine output< 25ml/hr, additional fluid boluses either colloid or crystalloid are given. Packed red-blood cells (PRBC) are included in resuscitation if the hemoglobin <7 g/dL. Fresh-frozen plasma (FFP) or platelets may be given at the request of the surgeon if surgical hemostasis is inadequate, international normalized ration (INR) >1.8 or platelets < 80,000 mL.

The GDT arm will have fluid therapy guided by the Edwards EV1000 system. First, blood loss will be replaced 1:1 volume with albumin. After this infusion, additional fluid will be given based on the patient's SVV. If this value is greater than 2 standard deviations of the baseline value more albumin will be given until SVV is less than or equal to no greater than 2 standard deviations above the baseline SVV. If the SVV is at baseline or not greater than 2 standard deviations from the baseline value, no additional bolus fluid will be given (Appendix 1). The maintenance crystalloid fluid will continue at 1cc/kg/hr that was begun in the LCVP phase. Group and protocol assignment will be maintained from the beginning of the reconstruction phase during the index operation, until after the patients are transferred to the PACU and receive standardized postoperative management at the discretion of the treating physicians.

During the intervention period, continuous non-invasive pulse wave analysis will be performed (Edwards EV1000) and the information stored in the monitor. Download is enabled to a USB port and memory stick. In the group assigned to standard management the monitor will be covered and the data derived from it will not be available to the anesthesia care team; this blinding will only be removed for the involved researchers at the completion of the study for retrospective analysis and comparison. At this time only research staff and anesthesia staff will have knowledge of patients randomization assignment.

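### Allocation is by envelopes in the operating room after resection, and no safeguard is described that keeps the next arm unknown or accounts for registered patients never assigned

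*Combined protocol and SAP*

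**What the plan says.** Consent and registration come before surgery. Section 15.1 requires an eligibility checklist and central registration: "Registrations must be submitted via the PPR Electronic Registration System". Section 15.2 then separates registration from allocation: "However randomization will not occur until the operating room". The method follows: "After the liver has been resected, intraoperative randomization will be done by envelopes". Section 4.1 says the same. Allocation is 1:1 and stratified by diagnosis (metastatic v primary disease).

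The randomized phase, in Section 4.1, "begins once the specimen has been delivered and hemostasis secured". Its first step in the goal-directed (GDT) arm is "First, blood loss will be replaced 1:1 volume with albumin", and the standard arm also replaces blood loss by volume.

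On knowledge of the arm, Section 4.1 states: "At this time only research staff and anesthesia staff will have knowledge of patients randomization assignment". Before resection, "Fluid boluses and/or vasoactive drugs are administered at the discretion of the anesthesia provider", within stated blood pressure, urine output and venous pressure targets.

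On accounting for patients, Section 13.0 says: "Randomized patients will not be replaced for any reason". Nothing comparable covers patients who are registered but never assigned.

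Section 9.0 places the covering of the EV1000 monitor in the standard group at the induction and intubation step, which precedes resection.

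**The concern.** When patients are allocated before any prognostic information emerges, a leak of the next arm gives staff little to act on. Here the decision to proceed to allocation is taken after the operation has revealed much of the patient's risk. Comparability of the arms therefore depends on the next assignment being unknowable until the patient is irrevocably committed. The plan gives a single word, envelopes, for that safeguard.

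If the next arm were known or guessable, some high-risk patients could go unassigned when a given arm was due, and the 30-day morbidity comparison would shift with no treatment effect. Such a patient would not stand out. Section 6.1 admits only open resections (including conversions from laparoscopy), so some registered patients will properly never be randomized, and no rule asks for the reasons to be listed.

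The monitor step in Section 9.0 adds a separate difficulty. Followed literally, the arm must be known at induction, while pre-resection boluses and vasoactive drugs are still discretionary.

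**Working it through.** **1. The passages side by side**

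- *Timing:* Sections 4.1 and 15.2 put allocation after resection; Section 9.0 lists an arm-dependent act at induction. Both cannot be followed as written.
- *Concealment:* Sections 4.1 and 15.2 do not say how the list is made, what the block sizes are, whether the envelopes are sealed, opaque or numbered, who holds or opens them, or whether opening is timed. Section 20.0 lists three appendices (fluid algorithms, complication grades, complication incidence); none of these titles concerns randomization.
- *Accounting:* Section 16.1 plans weekly registration reports, accrual monitoring and compliance audits, but no reconciliation of registered with randomized patients.

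**2. The plan's own sample size**

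Inputs (Section 14.0): 30% v 15%, two-sided 5%, 80% power. The mean rate is 0.225.

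- Uncorrected: [1.96·√(2·0.225·0.775) + 0.842·√(0.30·0.70 + 0.15·0.85)]² / 0.15² = 120.5, so 121 per arm.
- With continuity correction: (120.5/4)·[1 + √(1 + 4/(120.5·0.15))]² = 133.5, so 134 per arm and 268 in total.

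This agrees with the stated 270, which the point leaves unchanged.

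**3. How predictable an arm could be**

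Assumption: fixed permuted blocks within stratum, with past assignments known. In blocks of 4 there are six sequences. Two have two forced assignments and four have one, so (2·2 + 4·1)/24 = 1/3 are certain. For blocks of 2, 4, 6 and 8 the certain share is 50%, 33%, 25% and 20%, and the best guess is right 75%, 71%, 68% and 67% of the time.

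**4. Effect of steering when there is no treatment effect**

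Assumptions not in the documents: high-risk share h = 1/3; complication risk 50% in high-risk and 20% in other patients (overall (1/3)·50% + (2/3)·20% = 30%); 135 per arm; Pearson chi-square at 1.96, because Section 14.0 names no test for the primary endpoint; no interim look. Let k be the share of assignments known in advance and s the share of targeted patients held back.

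- GDT high-risk share when high-risk patients are held back from GDT: h(1 − ks)/(1 − h·ks). Held back: 135/(1 − h·ks) − 135.
- Standard high-risk share when other patients are also held back from standard (both ways): h/(1 − (1 − h)·ks). Held back: 135/(1 − (1 − h)·ks) − 135.
- Rate in an arm: 20% + 30% × its high-risk share.

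Blocks of 4, k = 1/3, s = 1/2, so ks = 1/6: GDT high-risk share = (5/18)/(17/18) = 0.294, rate 28.8%. Both ways: standard share = (1/3)/(8/9) = 0.375, rate 31.25%.

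Arm always known, k = 1, s = 1/2: GDT share = (1/6)/(5/6) = 0.20, rate 26.0%. Both ways: standard share = (1/3)/(2/3) = 0.50, rate 35.0%.

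Rejection probabilities are by exact enumeration of two binomials:

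| Scenario | GDT | Standard | Bias (points) | Two-sided type I error | Held back |
|---|---|---|---|---|---|
| No steering | 30.0% | 30.0% | 0 | 5.1% | 0 |
| Blocks of 4, one way | 28.8% | 30.0% | 1.2 | 5.6% | about 8 |
| Blocks of 4, both ways | 28.8% | 31.25% | 2.4 | 7.3% | about 8 + 17 = 25 |
| Arm always known, one way | 26.0% | 30.0% | 4.0 | 11.5% | 27 |
| Arm always known, both ways | 26.0% | 35.0% | 9.0 | 36.4% | 27 + 67.5, about 95 |

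**5. Sensitivity to the assumed risks**

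Arm always known, one-way steering, h = 0.30, high-risk rate 50% to 60%, overall rate kept at 30%, normal approximation:

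- 10% of high-risk patients held back: bias 0.6 to 0.9 points, type I error 5.1% to 5.3%.
- 30% held back: 2.0 to 3.0 points, 6.5% to 8.4%.
- 50% held back: 3.5 to 5.3 points, 9.9% to 16.4%, with 135·0.15/0.85 = about 24 patients held back.

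**The case against.** The case for the plan is substantial. Randomizing late has good reasons: open resection is an eligibility condition that may be settled only during surgery, the arms differ only after resection, and late allocation keeps the pre-resection phase common to both. Every consented patient is registered, so non-assignment leaves a trace, and Section 16.1 plans monitoring and audits. Pre-resection discretion is bounded by stated targets. The larger error rates need the next arm to be known every time and dozens of patients to be held back, which would be conspicuous. The registration system is described only for registration, with weekday office hours, so central allocation cannot be assumed to be available. Fully specified envelopes would close much of the gap.

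Nearly all of this stands. A reader might go further and infer that an unblinded team opens envelopes kept in the room and can see the next arm. The documents do not support that. They do not say who opens the envelopes or where they are stored. Section 4.1 lists research and anesthesia staff, not surgeons, as knowing assignments, and knowing a patient's arm once made is not knowing the next one.

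What remains is that none of these points supplies the missing concealment procedure, the accounting of unassigned patients, or an explanation of the induction-step monitor cover. The audits in Section 16.1 are run by the study team and are not directed at selective non-assignment.

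**Conclusion.** The point holds as a gap in the described procedure, and it is worth a cheap correction. The plan combines late allocation, when strong prognostic information is available, with envelopes whose handling is not described, and it has no rule for registered patients who are never assigned. The timing conflict between Section 9.0 and Sections 4.1 and 15.2 must be reconciled.

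The size is a range of exposure that rests wholly on assumed risks, block size and behaviour; it is not a forecast. Guessing in blocks of 4 does little harm. Under the base risks, 11.5% or more needs an arm that is always known and about 27 or more patients held back. A steeper risk gradient reaches 16.4% with about 24, again only with the arm always known. It would be wrong to read these figures as evidence that concealment failed, that the arms are not comparable, or that late randomization is itself a fault.

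**What to change.** Amend Sections 4.1 and 15.2 as follows.

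- **List:** the statistician generates it with randomly varying block sizes within the two diagnosis strata. It is held outside the operating room.
- **Release:** for an already registered patient, by log-in or by telephone through existing research staff, only after the room confirms that the specimen is out and bleeding is controlled. Each request is time-stamped, and the patient counts as randomized from that request.
- **Reserve:** sequentially numbered, sealed, opaque envelopes with a signed and timed opening log, for use outside office hours or if the registration system cannot allocate.
- **Accounting:** report every registered patient not randomized, with the reason. Limit any comparison with randomized patients to eligible patients who had an open resection, because patients not resected or completed laparoscopically differ legitimately.
- **Consistency:** reconcile the monitor-covering step in Section 9.0 with the time of randomization in Sections 4.1 and 15.2.

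The cost is a short amendment, one list, one call or log-in per case with a brief wait in the operating room, and a reserve procedure to maintain. The sample size stays at 270.
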